The proposed study is a proof of concept investigation to assess a new clinical application. Current technical challenges to the widespread adoption of PAE include identification and catheterization of arteries appropriate for embolization. Prostate arteries are frequently tortuous, with duplication or replacement and varying sites of origin, and due to the nature of the patient population, atherosclerosis further complicates identification and navigation. An imaging system that could assist with identification and catheterization has the potential to improve patient outcomes by facilitating more complete embolization, avoidance of non-target vessel occlusions, and reduction of radiation exposure time.

With the current proposal, the software application can be standardized and tailored to optimize safety and efficacy of prostate embolization, which has been shown in clinical trials to be an effective alternative treatment of enlarged prostate or bladder outlet obstruction.

Another advantage of the protocol is it may obviate the need for pre-procedure CT angiogram, further reducing radiation exposure and procedure time.

4) **Inclusion and Exclusion Criteria***

Inclusion criteria:

- 1) Patient is age 50 to 79, inclusive
- 2) Patients undergoing Prostate artery embolization for BPH or urinary retention
- 3) Patient has signed informed consent (able to consent).

Exclusion criteria:

- 1) Patients with biopsy proven prostate cancer
- 2) Patient weight of >300 lbs.

5) **Local Number of Subjects***

Approximately 50 patients will be enrolled at this investigator site no screening failures are anticipated since all 50 patients will receive PAE and cone-beam CT. Currently cone-beam CT is performed routinely for all PAE cases. 25 sequential patients will undergo PAE with 3D angiogram and Emboguide. This will be followed by 25 sequential patients who will undergo PAE with no 3D angiogram nor Emboguide.

6) **Study Timelines***

The study duration will be approximately one year from the start date. The enrollment will take about 8 months and data analysis will take about 3 months.

7) **Study Design/Procedures Involved**

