This is a single center prospective study. The patients eligible for the PAE for benign prostate hyperplasia will be offered the study and informed consent will be obtained. Once patient has been referred to Interventional Radiology (IR) and prior to the clinic visit with the IR physician, the records of the patient will be accessed for screening purposes. Patients will be recruited for participation in the study during routine consultation for the prostate embolization procedure. The main challenge of the PAE procedure remains the identification of the prostatic arteries and their super-selective catheterization. Contrast enhanced cone-beam CT (Dyna-CT) is already performed at our center as part of the PAE clinical protocol to reduce the risk of non-target embolization, especially to the rectal, bladder and penile vasculature. We will initially obtain a 3D rotational selective angiography of the internal iliac artery for study group. This dataset will be called the PLANNING dataset. We will assess if superimposing the pre-catheterization 3D dataset (in which the physician marks the prostate and its arterial feeders), can be used as an Emboguide tool along with overlay from a conventional DSA. This will be transmitted to live fluoroscopy and be used as an aid to catheterization of the prostatic arteries in the study group.

Study Group

The following parameters will be recorded for the study group:

- Time for catheterization as defined above
- Time for planning dataset for each side
- Total dose area product
- Dose for planning dataset for each side
- Dose area product only for fluoroscopy
- Total procedural time: **from access to closure**
- Amount of contrast medium used

Control Group

The following parameters will be recorded for the control group:

- Time for catheterization as defined above
- Total dose area product
- Dose area product only for fluoroscopy
- Total procedural time: **from access to closure.**
- Amount of contrast medium used

The tortuosity of the vessels will be graded in each case and will be categorized into:

- 1- Mild
- 2- Moderate
- 3- Severe

This will be graded visually for every case and will be noted on the case report forms. We will also study the arterial supply to the prostate gland with any anatomic variants including duplicated prostatic arteries or prostate arteries arising from less common branches such as common gluteal-pudendal trunk, obturator artery, and inferior gluteal artery in all patients.

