8) **Data Storage**

All data collected will be stored in a password protected database in a password protected computer of Interventional Radiology to which only the PI and study coordinator or other key research personnel have access.

Address: [name]
[name]
[name]

9) **Data Management***

The statistical analysis for the current study will be conducted as follows. The following variables and parameters will be collected:

- Time for catheterization

- Time for planning dataset for each side (This will be evaluated as the time from completion of the 3D angiogram to beginning of catheterization)
- Total dose area product,
- Dose for planning dataset for each side,
- Dose area product for fluoroscopy only,
- Total procedure time, and
- The amount of contrast media used.

Descriptive statistics (mean, median, range, and standard deviation) will be computed for the treatment group and the control group and values will be compared for the variables of interest.

Additionally, a statistical significance comparison between the study group (with guidance) and the control group (without guidance) will be computed for several parameters. Specifically, the differences in means and/or medians between the following variables and parameters will be analyzed using a T-test or a Mann-Whitney test (depending on normality of the distribution and other assumptions):

- Time for prostate artery catheterization for each group
- Total dose area product (this will include DAP from the planning dataset in the study group)
- Dose area product only for fluoroscopy,
- Total procedure time, and
- The amount of contrast medium used.

10) **Withdraw of Subject**

Patients can withdraw from the study at any time, without penalty or benefit. This study may be discontinued, without the patients consent, at any time by the study doctor, if he/she believes that participation in the study is no longer in their best interest.

11) **Risks to Subjects***

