Subjects will have one or more medical imaging studies (x-ray like films) which use radiation (emission or transmission of energy in the form of waves or particles). The tests or treatments include a whole body CT scan. To give an idea about how much radiation **the patients** will get, we will make a comparison with an every-day situation. Everyone receives a small amount of radiation that cannot be avoided each year. Some of this radiation comes from space and some from naturally-occurring radioactive forms of water and minerals. This research gives your body the equivalent of about 3 extra years' worth of this natural radiation. Subjects will be exposed to radiation as per their standard of care treatment. The investigational group will be subject to additional radiation for the 3D

planning dataset, however this in turn might reduce the duration of prostate artery catheterization leading to similar or reduced radiation if the 3D dataset was not used.

12) **Potential Benefits to Subjects***

There are no current direct benefits for patients, however there may be advantages to future patients if it is determined that this technology can obviate the need for pre-procedure CT angiogram and increase the safety of the procedure by reducing the risk of non-target embolization.

13) **Sharing of Results with Subjects***

The results will not be shared with subjects as there is no direct advantage to the patient and they are not related to clinical outcomes of the procedure.

14) **Setting**

Patients will be identify and recruited at PAC Radiology Clinic. The study procedures will be performed at UMHC.

15) **Recruitment**

Patients who require PAE will be referred by their Urologist or will visit an Interventional radiologist. This is a single center study. The patients eligible for the PAE for BPH will be offered the study and informed consent will be obtained. Patients will be recruited for participation in the study during routine consultation for the prostate embolization procedure.

16) **Confidentiality**

Subject study files will be stored in a double locked cabinet to which only the investigators and research team have access. The address is [name]. The only member(s) of the study team with access to it will be [name]. The data will be stored for up to 2-3 years after the study is completed and will be destroyed in accordance with university policies thereafter.

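### The study-only 3D planning angiogram would ordinarily add contrast, but Section 11 names only its radiation, Section 4 has no contrast-risk exclusion, and no study variable records a procedural adverse event (minor; cheap to improve)

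*Combined protocol and SAP*

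**What the plan says.** All references are to the combined protocol and SAP.

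- **The added step.** Section 7: "We will initially obtain a 3D rotational selective angiography of the internal iliac artery for study group". Section 5 gives this to 25 consecutive patients; the following 25 have neither the 3D angiogram nor Emboguide. Sections 5 and 7 describe contrast-enhanced cone-beam CT as routine for every PAE case, so the planning run comes on top of it. Section 12 expects no direct benefit to participants at present.
- **Its radiation.** Section 11: "The investigational group will be subject to additional radiation for the 3D" planning dataset. It adds that faster catheterization might offset this. Sections 7 and 9 log "Dose for planning dataset for each side".
- **Contrast.** Each group has one item, "The amount of contrast medium used" in Section 9's wording. For this and the other variables, "Descriptive statistics (mean, median, range, and standard deviation) will be computed for the treatment group and the control group", and contrast is among the five parameters tested between groups. Section 11 does not mention contrast, kidney injury or contrast reactions.
- **Eligibility.** Section 4 has two exclusions: biopsy-proven prostate cancer and "Patient weight of >300 lbs".
- **Safety data.** No parameter in Section 7 or 9 is an adverse event. Section 17 limits collection to information from the procedure, with no further visits. Section 10 lets the study doctor stop participation "if he/she believes that participation in the study is no longer in their best interest".

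**The concern.** The protocol recognises that the planning run adds an exposure and deals with the radiation part of it. Contrast is the other exposure that an angiogram ordinarily brings, and Section 11 does not mention it.

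Two consequences follow. First, a man aged 50 to 79 who is having PAE despite a prior severe contrast reaction or reduced kidney function meets every criterion. He could receive a research-only run, possibly on each side. Accepting him for PAE settles whether contrast is justified for his treatment. It does not settle whether more contrast is justified for a run with no stated direct benefit. Section 5 expects no screening failures because everyone will have PAE and cone-beam CT, which suggests that the second question is not asked separately.

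Second, if a contrast reaction or any other procedural adverse event occurred, clinical care might well detect it, but the study dataset has no field for it. Section 3 says the data might support a later grant proposal aimed partly at making PAE safer. The study would then hold no record of harm from its own procedures.

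**Working it through.** The plan states no figure on this point, so there is nothing to reproduce. The check is mostly a comparison of sections.

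**1. Is the run extra?** Yes. Section 7 assigns it to the study group, and Section 5 withholds it from controls. That it uses its own contrast is an inference from its being a selective angiogram. The protocol states neither a separate injection nor a volume.

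**2. How many runs?** Section 5 gives 25 study patients, and Sections 7 and 9 log planning data by side. The maximum is 25 × 2 = 50 runs, if both sides are planned in every patient.

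**3. Does the total include planning contrast?** Section 9 spells this out for radiation: "Total dose area product (this will include DAP from the planning dataset in the study group". There is no such note for contrast. However, Section 9 has two radiation measures, total and fluoroscopy only, so a clarification was needed there. Contrast has a single whole-procedure measure, and its natural reading is all contrast used.

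**4. What does a total without a planning split leave unknown?** Write a study patient's total as P + R, where P is planning contrast and R is the rest. A control's total is R alone. Then:

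study total − control total = P + (R in study − R in control)

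The net difference on the left is available under the current plan. P, and any saving in R from guidance, cannot be separated unless P is logged. With P logged, R = total − P for each study patient, and both parts can be described.

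**5. Could a contrast reaction be recorded?** Sections 7 and 9 list times, doses, contrast volume, vessel tortuosity and arterial anatomy. None is an adverse event. A same-day reaction would fall within Section 17's procedure-only scope but has no field. A later kidney effect falls outside that scope.

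**6. How much could 25 patients show?** With no events in 25 and every event recorded, the one-sided 95% upper limit is 1 − 0.05^(1/25) = 0.113, or 11.3%. Recording events would therefore document individual cases and would not establish safety. The documents give no contrast-harm rate.

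**The case against.** The strongest reply is that every participant has already been accepted for PAE, a contrast procedure, whichever group he is in. Clinical screening for kidney function and reaction history probably happens before enrolment, and an exclusion at the site's ordinary elective threshold might then remove nobody. This largely stands. It leaves only the incremental question of whether contrast that treatment does not need should be given to a patient at high contrast risk, so any threshold has to be set for that question.

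It is also fair to say that both groups receive contrast, so an event in a study patient could not be attributed to the planning run. The wider gap is that no adverse event of any kind is collected, including non-target embolization, which the technology is meant to reduce. Both points stand, and they argue for a general procedural adverse-event field that includes contrast reactions.

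A reader might infer four stronger things that the documents do not support:

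- **That planning contrast is left out of the total, biasing the comparison.** The single item is naturally read as the whole procedure.
- **That the study group receives more contrast overall.** Guidance might save later injections, as Section 11 suggests for radiation.
- **That patients are not told about contrast.** The consent form is not in the file; only Section 11's silence can be shown.
- **That high-risk patients go unscreened.** The protocol does not describe clinical screening, but that does not show there is none. Section 10 also leaves the study doctor discretion to stop, though it names no contrast or kidney criterion.

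**Conclusion.** The point holds as a minor one. A research-only angiogram, at most 50 runs in 25 patients, would ordinarily add contrast with no stated direct benefit. Section 11 names only its radiation, Section 4 has no criterion to withhold it from patients at high contrast risk, and no study variable would record a contrast reaction or other procedural adverse event. The primary outcome and the net contrast comparison are unaffected.

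This rests on one inference, that the planning run needs its own contrast. The volume, the net effect and the rate of harm are all unknown from the documents. No claim is made about the consent form or clinical screening. The case for acting is that the changes are cheap and improve both patient selection and the study record.

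**What to change.** 1. **Section 4.** Exclude from both groups, so that they stay comparable, patients with a prior severe contrast reaction. Also exclude those whose existing pre-procedure kidney result is below the level at which the site would give contrast that is not clinically needed. Use the records already opened for screening under Sections 7 and 20, with no new blood test.
2. **Sections 7 and 9.** Log planning-run contrast for each side, as is done for dose, and report it descriptively so that it can be separated from any later saving.
3. **Sections 7, 9 and 17.** Record same-day procedural adverse events, including contrast reactions, in both groups. List them without testing.
4. **Section 11.** Name contrast as an added study-group exposure.

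Optionally, list any creatinine taken in routine care within 7 days, with the number of patients who had a value. It would be incomplete and selectively sampled, and the consent and HIPAA wording would have to cover the chart check.

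**Cost.** The four changes need an eligibility criterion, a few form fields and wording edits. There is no added visit or test, so Section 19's commitment on subject costs is kept. A few patients may be excluded, and the kidney criterion cannot be applied where no result exists. The safety evidence from 25 patients would remain limited and could not attribute an event to the planning run.
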